# 7. RESEARCH QUESTION AND OBJECTIVES

Information on prescribing of filgotinib for UC under real-world clinical practice is scarce, specifically, in the context of the updated prescribing information and HCP Guide after implementation of Article 20 decisions on JAKi's.

Therefore, this longitudinal DUS aims to describe physicians' adherence to the prescribing information of filgotinib in real-world clinical practice and to evaluate the effectiveness of the aRMMs by assessing how HCPs prescribing filgotinib adhere to the information provided in the SmPC in conjunction with the information in the HCP Guide with a specific focus on aRMMs implemented after the EC Article 20 decision on JAKi's (i.e. after 10 March 2023).

The objectives of this study are as follows:

- a. To describe the characteristics of patients treated with filgotinib in terms of:
- Demographics (e.g., age and sex)
- Comorbidities and prior and current medication use
- b. To evaluate prescribers' adherence to the filgotinib aRMMs, specifically:
- Compliance with the recommended posology (average daily dose) and duration of use
- Compliance with recommendations for patient screening and laboratory monitoring prior to and during treatment
- Compliance to recommendations for use in patients with moderate to severe chronic renal impairment/end stage renal disease or severe hepatic impairment
- Compliance with recommendations for limitations of use, including:
  - Use in patients with risk factors for venous thromboembolism (VTE)
  - Use in patients aged 65 years and older
  - Use in patients with risk factors for cardiovascular (CV) disease
  - Use in patients with risk factors for malignancy

- Use in patients with risk factors for serious infections
- Use in patients with concomitant use of other potent immunosuppressants
- Use of live attenuated vaccines
- Contraindicated use
- Compliance with discontinuation of filgotinib treatment in patients experiencing VTE

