## 8.3.1. Patient Baseline Characteristics

Baseline variables are collected at the index date. These variables reflect the patient's demographics and status at the initiation of filgotinib treatment including relevant medical history at or prior to the index date. Baseline variables will include (as per availability by each registry):

- Age (at baseline)
- Sex
- Body mass index (BMI)
- Long-time smoking (for >10 years (Kristensen et al., 2023) (either current or past smoking)
- Date of UC diagnosis

- Severity of UC (for details, see Annex 3 Table 5)
- Renal impairment (for details, see Annex 3 Table 5)
- Hepatic impairment
- Type and number of previous UC treatments prior to filgotinib initiation
- Date of filgotinib initiation
- Initial filgotinib dose
- Diagnosis of active TB at index date
  - Date of diagnosis
- Active serious infection at index date
  - Date of diagnosis
- Current pregnancy (at index date)
  - Start of pregnancy
- Age  $\geq 65$  (at index date)
- History of atherosclerotic CVD (angina, coronary heart disease, myocardial infarction, congestive heart failure, stroke, peripheral arterial disease)
- Other CV risk factors (diabetes mellitus, hypertension, obesity/BMI  $\geq$  30 kg/m^2)
- Current malignancy
- History of malignancy
- Concomitant use of other immunosuppressants
- Diagnosis of viral hepatitis
  - Date of diagnosis
- Diagnosis of herpes zoster
  - Date of diagnosis
- Screening for viral hepatitis
  - Date of screening
- Laboratory measurements (measurement within ±1 month of filgotinib index date, or any time during follow-up)
  - absolute neutrophil count (ANC)
  - absolute lymphocyte count (ALC)
  - hemoglobin (Hb)
- Use of live-attenuated vaccines
- History of VTE
- Recent surgery (i.e. surgery within 1 month (Singh et al., 2023) prior to the index date or at any time during follow-up; see also Annex 3 Table 5)
- Reduced mobility (for details, see Annex 3 Table 5)
- Recent hospitalization (hospitalization within 1 month prior to the index date or at any time during follow-up; see also Annex 3 Table 5)
- History of blood clotting disorders
- Concomitant use of combined hormonal contraceptives
- Concomitant use of hormone replacement therapy

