## **Annex 3 Additional Information**

#### Variables of Interest

#### Table 5Variables of Interest and Their Availability by Registry

Variable	Availability in individual registries yes/no (additional comments)					
	ENEIDA (ES)	ICC (NL)	SWIBREG (SE)			
Variables assessed at baseline (start [index] date of filgotinib)						
Key patient characteristics						
Age: Date/year of birth	yes	yes	yes (Population Register)			
Sex	yes	yes	yes (Population Register)			
BMI	no (might be in medical report)	yes	yes (SWIBREG, but suboptimal coverage)			
Height	yes (not always available; might be in medical report)	yes	yes (SWIBREG, but suboptimal coverage)			
Weight	no (might be in medical report)	yes	yes (SWIBREG, but suboptimal coverage)			
Dx of UC	yes	yes	yes			
Date/year of Dx	yes	yes	yes			
Renal impairment (moderate to severe chronic kidney disease [stage 4 or 5])	yes (not always available; might be in medical report [and as described in the medical history of the patient])	yes (creatinine lab values are available)	yes (NPR via ICD10- and NCSP codes) (ICD10-codes: N17 - Acute renal failure N183 - Chronic kidney disease, stage 3 N184 - Chronic kidney disease, stage 4			

Variable	Availability in individual registries ves/no			
		(additional comments)		
	ENEIDA (ES)	ICC (NL)	SWIBREG (SE)	
	ENEIDA (ES)		SWIBREG (SE) N185 - Chronic kidney disease, stage 5 N189 - Chronic kidney disease, unspecified N19 - Unspecified kidney failure Y841- Kidney dialysis Z992 - Dependence on renal dialysis) NCSP-codes: DK001 - Installation of tunnelled hemodialysis catheter DK005 - Tunneled hemodialysis catheter replacement DR014 - Hemodiafiltration DR015 - Hemodialyis, acute DR016 - Hemodialyis, chronic DR020 - Continuous arteriovenous or venovenous hemofiltration DR025 - Preoperative hemodilution DR056 - Heparin-free dialysis DR060 - Home hemodialysis control DR061 - Home hemodialysis	
Severe hepatic impairment (Child Pugh C)	yes (not always available; might be in medical report)	yes	start yes (NPR via ICD-codes)	

Variable	Availability in individual registries yes/no (additional comments)			
	ENEIDA (ES)	ICC (NL)	SWIBREG (SE)	
UC treatment prior to initiation of filgotinib (specifically other JAKi's; advanced therapies; immunomodulators/immunosuppressants)	yes	yes	yes	
JAKi's	yes	yes	yes	
Advanced therapies – biologics (including TNFα inhibitors)	yes	yes	yes	
Advanced therapies – non-biologics	yes	yes	yes	

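### In Annex 3 Table 5, the Swedish code list for renal impairment goes beyond the row's own stage 4 or 5 chronic kidney disease label

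*Protocol*

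**What the plan says.** Section 7 (and the Abstract) lists among the adherence objectives: "Compliance to recommendations for use in patients with moderate to severe chronic renal impairment/end stage renal disease or severe hepatic impairment". It gives no stages or filtration-rate limits.

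The baseline variable list in Section 8.3.1 defers to the annex: "Renal impairment (for details, see Annex 3 Table 5)". The ENCePP checklist in Annex 2, item 6.2, also cites Annex 3 Table 5 as the place where outcomes are defined and measured.

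The row label in Table 5, shared by all three registries, is "Renal impairment (moderate to severe chronic kidney disease [stage 4 or 5", with the brackets closing there. The registry cells of that row then read as follows:

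- **SWIBREG:** available from the National Patient Register through ICD-10 and procedure codes. The list begins "N17 - Acute renal failure N183 - Chronic kidney disease, stage 3 N184 - Chronic kidney disease, stage 4", continues with stage 5, and then gives "N189 - Chronic kidney disease, unspecified N19 - Unspecified kidney failure". The dialysis-related codes include "DR015 - Hemodialyis, acute" and "DR025 - Preoperative hemodilution".
- **ICC:** available, with a note that creatinine values exist. No cut-off is given.
- **ENEIDA:** available, but not for every patient. The medical report or history may supply it.

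**The concern.** The row limits the variable to chronic disease at two named stages, and the only explicit code list in the row does not respect that limit. A programmer who takes the Swedish list at face value would flag patients with stage 3 disease, a past or current acute episode, a kidney code without a stage, or a blood-dilution procedure before surgery. All of them would appear under a heading that says stage 4 or 5 chronic kidney disease.

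Two things are at stake. The Swedish renal figure would not describe the group it names. It would also be less comparable with the Dutch and Spanish figures, although Section 8.1 says the common protocol was written to make the design more consistent across the three sources.

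**Working it through.** The protocol states no figure for renal impairment, so there is nothing to reproduce. The check compares the Swedish codes with the two wordings that govern them.

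**Inputs.** (a) The objective in Section 7: chronic impairment, moderate to severe, or end stage disease, with no stages given. (b) The Table 5 row label: chronic kidney disease, stage 4 or 5. (c) The SWIBREG code descriptions in the same row.

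**Code by code.**

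| Code | Own description | Fits the row label? | Fits the objective? |
|---|---|---|---|
| N184, N185 | chronic, stages 4 and 5 | yes | yes, on the label's reading |
| N183 | chronic, stage 3 | no, outside the bracket | cannot be settled; the objective names no stages |
| N189 | chronic, unspecified | stage unknown | stage unknown |
| N19 | kidney failure, unspecified | neither stage nor chronicity known | not known |
| N17 | acute renal failure | no | no, not chronic |
| DR015 | acute hemodialysis | no | no, not chronic |
| DR025 | preoperative hemodilution | no, names no kidney condition | no |
| DR020 | continuous hemofiltration | no chronic qualifier; needs checking | needs checking |

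**Can one reading save all three texts?** If stage 3 belongs, the bracket in the label is wrong. If it does not, N183 should not be on the list. Either way N17, DR015 and DR025 remain outside, because the label and the objective both say chronic.

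**Size.** It cannot be derived from the document. The following is an illustration only, and its prevalences are assumptions that come from no document. Take 500 patients, the per-registry ceiling in Section 8.5. Let stage 4 or 5 disease affect 0.5% to 1%, and let the additional codes bring in a further 0.5% to 4%.

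- Patients who meet the label: 500 × 0.005 = 2.5, up to 500 × 0.01 = 5.
- Patients flagged by the full list: 500 × (0.005 + 0.005) = 5, up to 500 × (0.01 + 0.04) = 25.
- Share of flagged patients who meet the label: lowest 0.005 / (0.005 + 0.04) = 11%; highest 0.01 / (0.01 + 0.005) = 67%.

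These results show only that a small true count leaves room for the additional codes to dominate. They do not forecast what the Swedish register would return. Section 8.4.3.2 says the National Patient Register holds inpatient and nonprimary outpatient care, so not every stage 3 patient need be coded there.

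**Study size.** Tables 3 and 4 in Section 8.5 do not use the renal definition and are unaffected.

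**The case against.** The strongest reply is that Table 5 is a table of availability. Its cells answer yes or no with comments, and the Swedish codes may only show what the register can supply. No sentence says that any single code makes a patient a case. The three stage codes are listed separately and could be split in analysis, and Section 8.7 leaves detailed methods to a common statistical analysis plan.

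Part of this stands. It is not established that an acute episode will be scored as chronic impairment, only that the list as written would allow it. The reply does not remove the conflict, however. Section 8.3.1 and checklist item 6.2 both treat Table 5 as the definition, and a label and a code list that disagree in one row are a contradiction in the protocol, not a detail left for later.

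A reader might also infer more than the text supports:

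- **That each registry has its own definition of the three wordings.** The moderate-to-severe wording and the stage 4 or 5 bracket sit in one label shared by all registries, so they cannot by themselves separate the registries. The divergence lies in the Swedish codes set against creatinine values in ICC and chart or history data in ENEIDA.
- **That compliance will be judged on patients to whom the recommendation does not apply.** The protocol's summary of the product information in Section 6 states no renal recommendation, so this cannot be tested from the document.
- **That differences between registries would be artefacts.** That is too absolute. Section 8.9 already warns that heterogeneous data may inflate or mask real differences, and Section 8.6.1 plans chart review for filgotinib patients in ENEIDA. The general caveat is fair, but it does not mention renal impairment and does not cure the mismatch.

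**Conclusion.** The point holds as an inconsistency inside one row of Annex 3 Table 5. Stage 3 (N183) contradicts the bracketed stages. N17, DR015 and DR025 contradict both the label and the chronic wording of the objective. N189 and N19 cannot be assigned to a stage. Stage 3 is not shown to lie outside the objective itself, which names no stages.

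The consequence is conditional. If the list is used as written, the Swedish count of renal impairment will contain patients outside the stated definition and will compare less well with the other two registries. How many cannot be said from the document. The effect is confined to one descriptive sub-objective of a study without hypotheses. It is worth correcting because the subgroup is a named adherence objective and the correction is cheap.

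**What to change.** - Reconcile the objective in Section 7 and the Abstract, the Table 5 row label and the Swedish code list to one stated stage range. Which range is right is for the sponsor and the registries to settle from the product information; this review does not choose it.
- Remove from the chronic definition the codes that are acute or non-renal by their own description: N17, DR015 and DR025. Check whether DR020 belongs, since it carries no chronic qualifier.
- Report stage 3, stage 4, stage 5 or dialysis, and stage unknown (N189, N19) as separate rows where a registry's data allow. Separate rows keep the table usable whichever range is adopted. ENEIDA may not be able to fill every row. In ICC a single creatinine value cannot show that impairment is chronic, so the limits of each source should be noted beside its figures. How creatinine is converted to a stage can be left to the statistical analysis plan.

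The cost is an edit to one annex row, its code list and the matching table shell. The downside is smaller counts and a few more rows.

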#### 8.4.3.2. National Patient Register and Prescribed Drug Register

The NPR provides information on all hospitalized (inpatient treated) patients (Ludvigsson et al., 2011), and all visits to nonprimary outpatient care (such as a visit to a gastroenterologist). Diagnoses are assigned by the physician, as well as date of discharge and discharging hospital for inpatient care, and hospital department. Diagnoses are coded according to the International Classification of Diseases (ICD), with version 8 used until 1986, version 9 from 1987 to 1996, and ICD10 since 1997. Due to routine validation and acquisition processes, data on hospital visits become available for research the earliest during the next calendar year. The PDR provides all filled prescriptions in Sweden from 1 July 2005, and may be used to aid correct classification of patients by their history of retrieved IBD therapies, or to define subcohorts based on treatment switches (Wettermark et al., 2007). A recent validation study has indicated that the coverage of the infusion drugs in the PDR is not optimal (Bröms et al., 2021).

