#### 8.4.3.3. The Contagious Disease Register

The Swedish Contagious Disease Register (SmiNet), established in 1971, provides events reported according to the Communicable Diseases Act and the Communicable Diseases Ordinance on diseases that have mandatory reporting in Sweden (e.g. TB).

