#### 8.4.3.7. The Total Population Register

The Total Population Register lists data on residency at a given point in time since it was founded in 1961, and dates of emigration/immigration for all subjects ever resident in Sweden since 1961. This register thus provides information on censoring (death and emigration) of patients (Ludvigsson et al., 2016).

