Immunomodulators /- suppressants (e.g. tacrolimus, azathioprine, mercaptopurine)	yes	yes	yes	
Other (aminosalicylates, corticosteroids)	yes (not always available; might be in medical report)	yes	yes	
Reasons for switching	yes	yes	yes (SWIBREG, good coverage for targeted therapies)	
Intolerance/adverse events	yes	yes	yes	
Lack of efficacy	yes	yes	yes	
Other	yes	yes	yes	
SmPC section 4.1: Indication				
Severity of UC (moderate to severe)	yes (some data in ENEIDA may be available or alternatively through chart abstraction [through proxies such as drug switching, addition of drugs, colectomy etc.])	yes (SCCAI, CRP, fecal calprotectin and if available radiologic and endoscopic information)	yes (Severity of UC based on proxies such as exposure to immunomodulators or different lines of targeted therapies (= moderate to severe UC) or proxies for flares (e.g., steroid prescriptions, steps in the treatment ladder, hospitalizations with UC as main diagnosis, UC-related surgery, extent/location of	

Variable	Availability in individual registries yes/no (additional comments)			
	ENEIDA (ES)	ICC (NL)	SWIBREG (SE)	
			disease in UC, history of prior biologic use, disease duration and UC-related treatment exposure)	
Date of severity assessment	yes (if defined by medical therapies)	yes	yes	
Date of filgotinib initiation (to ascertain new users) = index date	yes	yes	yes	
Age at index date	yes	yes	yes	
SmPC section 4.2: Posology (Induction treatment)				
Initial filgotinib dose (induction treatment)	yes (if not available, might be in medical report)	yes	yes	
SmPC section 4.3: Contraindications				
Active TB at index date	yes (if not available, might be in medical report)	yes	yes (SmiNet, Population Register)	
Dx date TB	yes (if not available, might be in medical report)	yes	yes (SmiNet, Population Register)	
Active serious infection (SI) at index date	yes (if not available, might be in medical report)	yes	yes (Population Register, PDR)	
Dx date SI	yes (if not available, might be in medical report)	yes	yes (Population Register, PDR)	
Current pregnancy at index date	yes (if not available, might be in medical report)	yes	yes (Medical Birth Register)	

Variable	Availability in individual registries yes/no (additional comments)				
	ENEIDA (ES)	ICC (NL)	SWIBREG (SE)		
Date of pregnancy	yes	yes	yes (Medical Birth Register)		
SmPC section 4.4: Special warnings and precautions for use (Box warning)					
(Age 65+)	yes	yes	yes		

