Variable	Availability in individual registries yes/no (additional comments)		
	ENEIDA (ES)	ICC (NL)	SWIBREG (SE)
			hospitalizations with IBD as the main diagnostic listing will be treated as flares)
Date of hospitalization	no (might be in medical report)	yes	yes (NPR)
Hx of blood clotting disorder or blood clots	no (might be in medical report)	yes (as part of medical history/comorbidity)	yes (NPR)
Concomitant use of combined hormonal contraceptives	no (might be in medical report)	no (but can be added)	yes (NPR)
Concomitant use of hormone replacement therapy	no (might be in medical report)	no (but can be added)	yes (NPR)
SmPC section 4.6: Fertility, pregnancy and lactation			
Advice on contraception in women of childbearing potential	no	no	no
Breastfeeding	no (might be in medical report)	no (but can be added)	no
	Variables assessed during follo	w-up	
Filgotininb treatment status			
Discontinuation	yes	yes	yes (SWIBREG, PDR)
Date of discontinuation	yes	yes	yes (SWIBREG, PDR)
SmPC section 4.2: Posology (Maintenance treatment)			
Maintenance filgotinib dose (after a maximum of 22 weeks of induction treatment)	yes (if not available, might be in medical report)	yes	yes (PDR)
SmPC section 4.3: Contraindications			

Variable	Availabil (ad		ries
	ENEIDA (ES)	ICC (NL)	SWIBREG (SE)
Tuberculosis (TB)	yes (if not available, might be in medical report)	yes	yes (SmiNet)
Dx date TB	yes (if not available, might be in medical report)	yes	yes (SmiNet)
Serious infection (SI)	yes (if not available, might be in medical report; a proxy definition of infection severity can be used to align with the definition of the other registries, based on information available from an eCRF field on the outcome of the infection [such as death, hospital admission])	yes (infections that lead to hospitalization or intravenously administrated antibiotic or antiviral medication)	yes (ICD-10 codes as recorded in the NPR or the 'infectious disease register' [for tuberculosis] including overall codes for e.g. sepsis or septic shock or for specific infectious disease categories being the main or contributory diagnostic listing for a hospitalization)
Dx date SI	yes (if not available, might be in medical report)	yes	yes (NPR)
Pregnancy	yes (if not available, might be in medical report)	yes	yes (Medical Birth Register; could be retrieved following child birth)
Date of pregnancy	yes	yes	yes (Medical Birth Register; could be retrieved following child birth)

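### Table 5 sources three Swedish variables (active serious infection at index, TB screening, hormone use) from registers that the protocol does not describe as recording them

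*Protocol*

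**What the plan says.** Section 8.3 and Section 8.4.3 send the reader to Annex 3, Table 5 for the variables and their availability. The ENCePP checklist (item 6.2) names the same table as the place where outcome definition and measurement are described. The relevant Swedish entries are:

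- Active serious infection at index, and its diagnosis date: "yes (Population Register, PDR".
- Serious infection during follow-up: mainly ICD-10 codes in the NPR, with the infection "being the main or contributory diagnostic listing for a hospitalization".
- Active TB at index, and its diagnosis date: SmiNet plus the Population Register.
- Screening for TB, and its date: yes, from SmiNet. The neighbouring Swedish rows for herpes zoster and viral hepatitis screening say no.
- "Concomitant use of combined hormonal contraceptives", and the hormone replacement row below it: yes, from the NPR.
- Diabetes, hypertension and obesity/BMI as cardiovascular risk factors: yes, from the NPR. A separate BMI row names SWIBREG, with incomplete coverage.

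The registers themselves are described in Section 8.4.3. The Total Population Register "lists data on residency at a given point in time since it was founded in 1961", and its role is summed up as follows: "This register thus provides information on censoring (death and emigration) of patients". SmiNet provides reported events "on diseases that have mandatory reporting in Sweden (e.g. TB". The NPR covers inpatient care and "all visits to nonprimary outpatient care (such as a visit to a gastroenterologist", with physician-assigned ICD diagnoses. On dispensing: "The PDR provides all filled prescriptions in Sweden from 1 July 2005".

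**The concern.** A source cell in this table tells the Swedish analysts where to look. If the named register does not record the variable, following the table gives a wrong answer rather than a missing one.

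The affected variables serve objectives named in Section 7. Active serious infection at index is a contraindication. TB screening belongs to screening compliance. Hormonal contraceptives and hormone replacement are VTE risk factors listed in Section 6, so they help define the high-risk group whose maintenance dose is examined separately (Section 8.7).

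For serious infection there is a second problem. The same concept would be measured one way at index and another way in follow-up, so the two Swedish figures could not be compared.

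For TB screening the danger is a misreading. Section 8.7.1.3 expects missing baseline values to be rare, so the absence of a SmiNet record could be reported as failure to screen when it only means that nothing was notified.

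**Working it through.** The protocol gives no figure for this point, so the check sets each Swedish cell of Table 5 against the register descriptions in Sections 8.4.3.2 to 8.4.3.7.

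| Variable (Swedish column) | Source named in Table 5 | What the protocol says that source holds | Fit |
|---|---|---|---|
| Active serious infection at index, and date | Population Register, PDR | Residency, migration and censoring; filled prescriptions | Neither is described as holding a diagnosis or its date |
| Serious infection in follow-up | NPR hospital diagnoses; infectious disease register for TB | ICD diagnoses from hospital and specialist care; notified disease | Fits, but differs from the index row |
| Active TB at index, and date | SmiNet, Population Register | Notified disease; residency | SmiNet fits, the Population Register does not |
| TB screening, and date | SmiNet | Notified disease | A negative screen is not a notified event |
| Combined hormonal contraceptives; hormone replacement | NPR | Visits, admissions, diagnoses | Dispensed drugs are in the PDR |
| Diabetes, hypertension, obesity | NPR | Diagnoses outside primary care | Can be held, but incompletely |

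**Count.** Two rows for index infection, two for TB screening and two for hormones make 2 + 2 + 2 = 6 rows with an unsuitable source. Two further rows (active TB and its date) name one register that fits and one that does not.

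**Serious infection at index.** The PDR could in principle act as a proxy through antibiotic dispensing. Table 5 does use it that way, but only for acute infection in follow-up and only together with the NPR. It does not do so for serious infection, which in follow-up is defined by hospitalisation.

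**TB screening.** No linked Swedish register is described as recording that a screening test was done. The Dutch column already says no, so Spain is the only registry with a usable entry, although the table implies two.

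**Diabetes, hypertension and obesity (secondary).** The NPR is a suitable source for events treated in hospital, such as infarction or stroke. For conditions managed only in primary care it will miss cases, and the documents give no sensitivity.

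An illustration of scale can use the protocol's own precision example, with p = 10% and n = 300. SE = √(0.10 × 0.90 / 300) = 1.73%, and 10% ± 1.96 × 1.73% gives 6.6% to 13.4%. Both agree with Section 8.5.

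Now assume perfect specificity and a capture sensitivity s, which is an assumption and not a documented value. The observed proportion is s × 10%, and the shortfall in standard errors is (10% − s × 10%) / 1.73%:

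- s = 0.4: reads 4%, short by 3.5 SE
- s = 0.6: reads 6%, short by 2.3 SE
- s = 0.8: reads 8%, short by 1.2 SE
- s = 0.9: reads 9%, short by 0.6 SE

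The range shows that under-capture could outweigh sampling error or be negligible, depending on a sensitivity that the protocol does not state.

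**The case against.** The best defence is that these are labelling slips in an annex. Section 8.4.3 bases Swedish baseline and follow-up data on SWIBREG, the NPR and the PDR, all of which are linked. Section 8.4.3.1 says the linkage captures the safety endpoints of interest. Population Register may simply be a slip for Patient Register, and a programmer looking for hormone use would probably turn to the PDR anyway. This stands as far as repair is concerned: for infection and hormones the right data are already in the linkage. It does not remove the need for correction, because Table 5 is the only place where the source of each variable is fixed.

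It is also fair to say that TB screening has limited reach. The baseline list in Section 8.3.1 names hepatitis screening but not TB screening, Section 8.7 sets out no TB-screening analysis, and Section 8.9 admits that not every registry captures everything. The Table 5 entry is nevertheless wrong on the protocol's own description of SmiNet, and screening compliance is an objective.

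Finally, supplementing NPR diagnoses with drug dispensing is a choice of case definition that may properly be settled at the analysis-plan stage. That is why the cardiovascular risk factors are secondary here.

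**Conclusion.** Three Swedish variables, in six rows of Table 5, are assigned to registers that the protocol does not describe as recording them, and serious infection is measured differently at index and in follow-up. This should be fixed. The conclusion rests on the register descriptions in Section 8.4.3 as written and on Table 5 being applied as written.

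A reader might infer three stronger things that the documents do not support:

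- That Sweden would report almost no TB screening or hormone use whatever prescribers did. This is a prediction. Section 8.4.3.3 does not say whether positive screening results are notified, and the PDR is available to anyone who looks past the cell.
- That the NPR cannot hold diabetes, hypertension or obesity. It holds ICD diagnoses from hospital and specialist care, so the defect is incomplete capture. The size of any understatement of the high-risk share cannot be derived from the protocol, which gives neither prevalences nor sensitivities.
- That all Swedish contraindication data are unsound. Pregnancy is taken from the Medical Birth Register, and active TB names SmiNet, which fits. Of the three contraindications, only active serious infection lacks a suitable source.

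**What to change.** In the SWIBREG column of Table 5:

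1. Take active serious infection at index, and its date, from the NPR with the hospitalisation definition used in follow-up, in a stated window before the index date.
2. Remove the Population Register from the serious-infection and active-TB rows.
3. Set TB screening and its date to no / not evaluable, as is done for herpes zoster and hepatitis screening, unless a register that records screening is named.
4. Move combined hormonal contraceptives and hormone replacement to the PDR.

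Secondary and also cheap: define diabetes and hypertension as an NPR diagnosis or a PDR dispensing of the corresponding drug class, or else state in Section 8.9 that cases managed in primary care are under-captured. Reconcile the BMI row (SWIBREG) with the obesity/BMI row (NPR), keeping the BMI threshold of 30 kg/m² from Section 8.3.1.

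The cost is a table edit and matching code lists, since every register needed is already in the linkage. The drawbacks are that TB screening can then be assessed only in Spain, that a pre-index window has to be chosen and justified, and that drug-based definitions will add some false positives, chiefly for hypertension.
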